5.1.6.2.4. Infusion Reaction of SHR-1210

As SHR-1210 is one fully humanized monoclonal antibody, the possibility of infusion

or allergic reaction is low, and preventive medication is not needed prior to infusion. Allergic reaction is most likely to occur within 24h after infusion. Once the allergic reactions occur, the infusion should be slowed down or interrupted based on the condition, and clinical supportive treatment is needed. The preventive medication should be given prior to the subsequent doses. The allergic reactions are possibly characterized by fever, intolerance of cold, chills, headache, rash, pruritus, arthralgia, low or high blood pressure, or bronchospasm. All the Grade 3 or 4 infusion reactions should be reported to the sponsor within 24h, and reported as SAE in case of meeting the criteria for SAE. See detailed reporting methods in Section 8.2.

Response to allergic reactions should be based on the medical practice and guidelines of the study site. See recommendations for the treatment of infusion reactions in Table 7.

Table 7. Recommendations for the Treatment of Infusion Reactions

| CTCAE Grade | Clinical symptoms | Clinical treatments | SHR-1210 treatment |
|----------------|--|--|--|
| Grade 1 | Mild transient reactions | Bedside monitor, close monitoring till recovery. Preventive medication is recommended prior to the infusion afterwards: Diphenhydramine 50 mg, or equivalent and/or Acetaminophen 325-1000 mg, administered at least 30 mins before the infusion of SHR-1210. | Continue. |
| Grade 2 | Moderate reactions requiring treatment or dose interruption that can be rapidly relieved after symptomatic treatment (e.g., antihistamine drugs, non-steroid anti-inflammatory drugs, anaesthetics, bronchodilators, intravenous infusion, etc.) | Normal saline i.v. infusion, Diphenhydramine 50 mg i.v. or equivalent and / or Acetaminophen 325-1000 mg; Bedside monitor, close monitoring till recovery. Corticosteroids or bronchodilators can be considered if clinically required; The dose of study drug administered will be recorded in the source documents; Preventive medications are recommended prior to the infusion afterwards: Diphenhydramine 50 mg, or equivalent and/or Acetaminophen 325-1000 mg, administered at least 30 mins before the infusion of SHR-1210. Cortisol (equivalent to 25 mg hydrocortisone) can be used if necessary. | Interrupted temporarily. Resuming the medication after symptoms disappear at 50% of the initial infusion rate. If there is no complication within 30 minutes, increase to the original 100% infusion rate. Closely monitor. If relapse, the current dose of SHR-1210 can not be given again. |
| Grade ≥ 3 | Grade 3: serious reactions, no rapid relief after treatment and/or dose interruption; or relapse after remission; sequela occurred requiring hospitalization. Grade 4: life threatening | The infusion of SHR-1210 shall be immediately discontinued; Start normal saline i.v. infusion. 
 Bronchodilators, 0.2-1 mg 1:1000 epinephrine solution (s.c.), or 0.1-0.25 mg 1:10000 epinephrine solution (i.v.), and/or diphenhydramine 50 mg combined with methylprednisolone 100 mg or equivalent drugs (i.v.); Comply with guidelines for allergic reactions of the study site; Bedside monitor, close monitoring till recovery. | Discontinued permanently. |

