5.1.6.1.4. Criteria for Permanent Discontinuation of SHR-1210

The study drug SHR-1210 must be discontinued permanently when the following conditions occur:

- Any Grade 2 drug-related uveitis, ophthalmodynia and blurred vision that has no response to local therapy and is not recovered to Grade 1 after delayed dose; or the above AE requiring systemic therapy;
- Any Grade 3 drug-related non-cutaneous AE lasting for >7 days, except the following:
 - When any Grade 3 drug-related uveitis, myocarditis, encephalitis, pneumonia, bronchospasm, hypersensitivity or infusion reaction occurs, the study treatment must be terminated;

- In case the drug-related endocrine disorders can be sufficiently controlled only with hormone replacement therapy at physiological doses, the treatment does not need to be terminated;
- The treatment does not need to be terminated for Grade 3 drug-related abnormal laboratory examination, however, the study drug must be terminated for Grade 3 thrombocytopenia >7 days or related with bleeding.
- Hepatotoxicity meeting the following:
 - AST or ALT >10 times of ULN for over two weeks;
 - ALT or AST > 15 × ULN;
 - TBIL >8 times of ULN for subjects with elevated TBIL at baseline, >5 times of ULN for subjects with normal TBIL at baseline.
- Any Grade 4 drug-related AE or abnormal laboratory examination, except the following:
 - Grade 4 granulocytopenia is less than 7 days;
 - Grade 4 lymphopenia or leukopenia;
 - Isolated Grade 4 elevated amylase or lipase, without symptoms or clinical manifestations of pancreatitis;
 - Isolated Grade 4 electrolyte imbalance/abnormality without clinical sequelae that could be corrected through supplements/appropriate management within 72h after occurrence;
 - If Grade 4 drug-related endocrine disorders that can be sufficiently controlled only with hormone replacement therapy at physiological doses, the treatment does not need to be terminated.
- The study treatment must be terminated if SHR-1210 needs to be delayed for >12 weeks, except the following:

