8.4. AEs of Special Interest

For the AE of special interest (SIE) specified in the study protocol (as below), investigators need to fill in the "Adverse Event of Special Interest Report Form in Hengrui Clinical Study" within 24h after the event is known, and report to the sponsor. If it is SAE at the same time, please also fill in "Serious Adverse Event Report Form".

- \geq Grade 3 infusion reaction
- \geq Grade 3 immune related AE
- AEs that meet the criteria defined in Section 8.4.1 (Liver Function Test [LFT] Abnormalities)

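### In Table 7 an infusion reaction that clears and returns on restart fits both the Grade 2 and the Grade 3 row, and the protocol does not say which one governs SHR-1210 and reporting

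*Protocol*

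**What the plan says.** Protocol section 5.1.6.2.4 sets out the handling of infusion reactions to SHR-1210 in Table 7, one row per grade.

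- **Grade 2, description.** "Moderate reactions requiring treatment or dose interruption that can be rapidly relieved after symptomatic treatment".
- **Grade 2, SHR-1210 column.** The infusion is interrupted, then: "Resuming the medication after symptoms disappear at 50% of the initial infusion rate". If nothing happens in the next 30 minutes the full rate is restored. If the reaction comes back: "If relapse, the current dose of SHR-1210 can not be given again".
- **Grade 2, clinical-treatment column.** "Preventive medications are recommended prior to the infusion afterwards".
- **Grade 3, description.** After an opening reference to serious reactions, the cell lists "no rapid relief after treatment and/or dose interruption; or relapse after remission; sequela occurred requiring hospitalization". For Grade 3 and above the SHR-1210 column gives permanent discontinuation.

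Three other rules depend on the grade.

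- Section 5.1.6.1.4, for a list of Grade 3 drug-related events: "hypersensitivity or infusion reaction occurs, the study treatment must be terminated".
- The text of section 5.1.6.2.4: "All the Grade 3 or 4 infusion reactions should be reported to the sponsor within 24h".
- Section 8.4 makes any infusion reaction at or above the level "Grade 3 infusion reaction" an AE of special interest, with its own form due to the sponsor within 24 hours.

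**The concern.** The Grade 2 row plans for a reaction that settles, is rechallenged and returns. The Grade 3 description in the next row names the return of a reaction after it has remitted. A site with such a patient can find the event in either row, and the rows do not lead to the same place.

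Two things are at stake. The first is the individual patient. Under one row this infusion is lost and nothing bars the next; under the other SHR-1210 is over. The second is reporting. The 24-hour report and the special-interest form are triggered at Grade 3, so the row a site picks decides whether the sponsor hears of the event promptly.

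**Working it through.** No arithmetic underlies the point. The check is a comparison of texts.

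1. **Does the Grade 2 relapse clause describe a return after remission?** Yes. The restart is conditional on symptoms having disappeared, and the relapse clause follows the restart. Any relapse it covers therefore comes after symptoms cleared.
2. **Does the Grade 3 description exclude a relapse on restart?** No. The relapse item is joined by a semicolon and the word or. It carries no condition about rechallenge, infusion rate or the severity of the second episode.
3. **What does each row do with SHR-1210?** The Grade 2 row rules out the current dose and does not mention later ones. Its premedication advice looks ahead to later infusions, but it is written for all Grade 2 reactions, relapsed or not. The Grade 3 row ends SHR-1210.
4. **Do the general rules settle it?** They follow the grade and so pass the ambiguity on. Under Grade 2, section 5.1.6.1.2 delays the dose, and section 5.1.6.1.3 generally allows resumption once a drug-related event is back to Grade 1 or baseline. Under Grade 3, section 5.1.6.1.4 requires termination and sets infusion reactions apart from its seven-day duration condition.
5. **Does reporting depend on the grade?** Yes. The 24-hour report in 5.1.6.2.4 and the special-interest listing in 8.4 both start at Grade 3.
6. **Is there a rule of precedence?** None was found. Table 7 does not tell the site to regrade a relapsed Grade 2 reaction, and 5.1.6.1.4 does not refer to relapse on restart.

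**How often it could arise.** The protocol gives no rate for infusion reactions or for relapse on restart. Section 5.1.6.2.4 calls the possibility of an infusion or allergic reaction low. In section 1.2.2.1 (258 phase I patients) infusion reaction is not named among any-grade AEs at 10% or more, nor among Grade 3 or higher AEs at 2% or more. If those lists were complete and carried over to this trial, the ceilings would be 0.10 × 43 = 4.3 patients with any infusion reaction and 0.02 × 43 = 0.86 with one of Grade 3 or higher. Relapses on restart would be a subset of the reactions. This is only indicative: the lists are worded as the main events, they come from other SHR-1210 studies, and they include fever and rash, which 5.1.6.2.4 names as possible signs of an allergic reaction to the infusion.

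**The case against.** The strongest case on the other side has four parts.

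- **The two cells can be read in sequence.** Withholding the current dose is compatible with permanent discontinuation: stop this infusion, regrade to Grade 3, then stop for good. A reader might infer that the table orders opposite actions, and that goes too far. No sentence says that a relapsed patient is dosed again. But the Grade 2 cell does not send the site to the next row either. It gives its own, narrower instruction and stops there.
- **Severity may separate the rows.** Grade 2 opens with moderate reactions and Grade 3 with serious ones, so the relapse item may be meant only for serious reactions. The punctuation in that cell is loose enough to allow this, but the limit is not written.
- **Table 7 is advisory.** It is headed as recommendations, and 5.1.6.2.4 defers to site practice and guidelines. It would be wrong to say that the table by itself requires permanent discontinuation. The binding rule is in 5.1.6.1.4 and follows from the grade, which is the unsettled part. That section also lets the investigator stop SHR-1210 where continuing would bring major risk. This softens the safety concern but does not settle the grade.
- **The analysis tables use another source.** A reader might infer that the event moves in or out of the Grade 3 or higher incidence tables. The protocol does not support that. Sections 8.1.2 and 10.4.9.1 take severity from NCI-CTCAE v4.03, whose text is not reproduced in the protocol, so a tabulation error would arise only if sites graded from Table 7's symptom column.

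**Conclusion.** The point holds as an inconsistency of wording in a safety rule. An infusion reaction that clears and returns on restart meets the Grade 2 relapse clause and, as written, a Grade 3 criterion. The first removes only the current SHR-1210 dose and says nothing of later ones. The second ends SHR-1210, and 5.1.6.1.4 makes that mandatory. The same event can also be handled differently for the 24-hour report and as an AE of special interest.

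It is likely to be rare, and no frequency can be derived from the protocol. It does not affect the primary endpoint, the two-stage decision or the sample size. The conclusion assumes that the relapse item in the Grade 3 cell is a criterion in its own right, as its wording suggests. If it was meant only for serious reactions, the overlap shrinks, but the text still needs to say so.

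**What to change.** Reconcile the Grade 2 and Grade 3-and-above rows of Table 7 with sections 5.1.6.1.4, 5.1.6.2.4 and 8.4, consistently with NCI-CTCAE v4.03 grading. A relapse on restart should have one grade, one SHR-1210 action and one reporting route. In practice, either the Grade 2 relapse instruction or the Grade 3 description changes. If a severity limit on relapse is intended, state it in the cell, and say what follows for later doses. The sponsor decides which clinical rule applies.

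The cost is about one table cell in a protocol amendment and a notice to the site. No new data are needed and no analysis changes.

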5.1.6.2.5. Rules for Management of Adverse Events of Apatinib

Management of apatinib-related adverse events can be performed according to clinical practice in this study protocol, and the following recommendations are provided for your reference.

1. Hand-and-foot syndrome

Hand-foot syndrome (HFSR): is palmar-thenar hypoesthesia or erythema at extremities, one of the cutaneous toxicity, is more obvious at the pressed or forced

area when it occurs. It may appear in tumor patients during chemotherapies or molecular targeted therapies. HFSR is characterized by numbness, hypoesthesia, paresthesia, stabbing pain, analgesia or swelpain, cutaneous swelling or erythema, desquamation, chapping, hardened blister or serious pain, etc.

Grading:

Grade 1: numbness, dysesthesia/paresthesia of hand and/or foot, painless swelling or erythema and/or discomfort that has no effect on normal activities.

Grade 2: painful erythema and swelling of hand and/or foot and/or discomfort that affects patient's daily life.

Grade 3: moist desquamation, ulcer, blister or serious pain of hand and/or foot and/or serious discomfort that makes patient unable to work or engage in daily activities. Intense pain, loss of skin function, comparably rare.

Symptomatic treatment and measures:

Recommended some necessary supportive treatments include intensive skin care, keeping skin clean to avoid secondary infection; avoiding pressure or scratching; using moisturizing cream or lubricant, including local use of lotion or lubricant containing urea and corticosteroids; and local use of anti-fungal or antibiotic therapy when necessary.

Note: If \geq Grade 3 hand-foot syndrome occurs for consecutive three times, with an aggravating tendency, the administration of apatinib should be terminated.

2. Hypertension

Subjects should be enrolled strictly in accordance with the requirement of blood pressure in the inclusion/exclusion criteria, subjects with hypertension can achieve controlled through adjustment of the dose of antihypertensive agents or adding of new antihypertensive agents prior to taking the study drugs, the blood pressure should be controlled within 140/90 mmHg.

Monitoring and management of hypertension:

The blood pressure should be monitored everyday (based on the average of BP readings acquired from ≥ 2 measurements) after the initiation of apatinib mesylate treatment.

Once hypertension occurs, the following treatment can be given: Angiotensin II receptor blockers (ARB), angiotensin-converting enzyme inhibitors (ACEI), β receptor blockers, etc. Or combined use of the aforementioned drugs.

If subjects have hypertension or exacerbation of hypertension during administration, should take following actions:

- 1) Adjusting the administration of study drugs as specified in the protocol (see Section 5.1.6.1.5);
- 2) Starting to take antihypertensive agents or adjusting the dose.

Subjects are required to keep a detailed record of their daily blood pressure in subjects'

diary. If they are taking hypertension drugs at the same time, they are required to keep a detailed record of the drug name, dosage, method and frequency of use, and related complaints or symptoms of discomfort.

The hypertension treatment drugs are recommended as below:

- 1) Angiotensin-converting enzyme inhibitors (ACEI);
- 2) Angiotensin II receptor antagonists (ARB);
- 3) dihydropyridine calcium channel antagonists;
- 4) β receptor blockers.

Use of diuretics is not recommended for anti-hypertensive therapy; nicardipine, diltiazem and verapamil with CYP3A4 inhibitory effect are prohibited. Apatinib mesylate should be discontinued in patients with hypertensive crisis.

3. Proteinuria

Proteinuria should be closely monitored for all the patients throughout the treatment, and intensively monitored in patients who have history of hypertension; the 24-hour urine protein quantification must be performed for the subjects with urine protein $\geq 2+$ for consecutive two times.

Note: Apatinib mesylate shall be discontinued in case nephrotic syndrome occurs.

4. Hemorrhage of digestive tract

Active symptomatic treatment should be given when gastrointestinal hemorrhage occurs, including persistently positive result of fecal occult blood, haematemesis or bloody stool. The subjects who are judged as upper gastrointestinal hemorrhage should be fasted and given acid suppression agents, drugs for gastric mucosa protection hemostasis (Transamin, Reptilase, etc.) treatment, and octreotide can be used when necessary; hemostasis, blood transfusion and supportive treatments will be given for those with lower gastrointestinal hemorrhage; surgical assistance may be required immediately if the hemorrhage can not be controlled. Adjustment of medication in accordance with the principle in Section 5.1.6.1.5 in the protocol.

5. Thrombosis

Apatinib mesylate should be discontinued immediately for any arterial thrombosis (e.g., cerebral ischemia, stroke, angina pectoris, myocardial infarction, etc.). Apatinib mesylate should be temporarily discontinued in case symptomatic venous thrombosis occurs.

Symptomatic treatment, surgery or anticoagulants should be given immediately for thrombotic symptoms.

5.2. Management, Distribution and Recovery of Drugs

5.2.1. Drug Preparation

The study drug should be prepared by qualified person in accordance with the

brochure of study drug.

5.2.2. The Disposal of Remaining Drugs

Investigators or their authorized representatives should record the date and dose of the drug administered for each subject. The residual investigational products will return to the sponsor regularly for destruction after being counted. If the remaining drugs should be destroyed at study sites, investigators must ensure the destruction is in accordance with applicable environmental laws and regulations, unit policies and other applicable terms, also need to provide relevant procedures for destruction. All the destructions should be well recorded.

5.3. Concomitant Therapy

All treatments and medications (excluding solvent) used from 28 days prior to the signature of informed consent form to the end of safety follow up should be recorded in the eCRF with raw data strictly in accordance with the GCP. If adverse events occur, the subject should be closely observed, as well as actively given symptomatic treatment if necessary, which is fully documented in medical records, and the drug and non-drug treatment used shall be recorded and specified in the eCRF. Only the concomitant medication/therapy that is used to manage the study drugs related AE/SAE should be recorded after the above collection periods.

5.3.1. Prohibited or Cautiously Used Medications and Treatments During the Study

5.3.1.1. Drugs and Therapies Prohibited for All the Subjects During the Study

Subjects are prohibited from using modern traditional Chinese medicines that have been approved by the NMPA (or by regulatory authorities in other countries) for the indication of HCC (including but not limited to Delisheng Injection, Kanglaite Injection, Aidi Injection, Huaier Granule and Ganfule Tablets) and immune-modulators (including but not limited to interferon, interleukin-2, thymosin, etc.) during the study.

During the treatment period of this study, subjects are not allowed to receive any local therapies against liver tumor lesion and targeted lesion (except palliative local therapies described in Section 5.3.2.4), and other systemic antitumor therapies, such as chemotherapies, molecular targeted therapies, hormone therapies, immunotherapies, and so on.

Subjects are not allowed to use other investigational products for antitumor therapy during the treatment period of this study.

Section 4.2 (Exclusion Criteria) of the protocol describes other drugs prohibited in this study.

5.3.1.2. Drugs Prohibited for Subjects Given SHR-1210 During the Study

Subjects are not allowed to receive immunosuppressive therapies (such as Thymalfasin, interferon, interleukin-2 and other immunologic agents) simultaneously during the treatment period of this study (except management on the treatment-related

adverse events).

Systemic corticosteroid can be used at the dose of >10mg/day (Prednisone or equivalent), except for treatment-related AEs treatments or short-term preventive therapies.

Vaccination of live vaccine are prohibited within 4 weeks prior to the first dose of study drugs until 60 days after the last dose.

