17. Current use of immunosuppressive medication, or systemic corticosteroid therapy to achieve the objective of immunosuppression (Prednisone at the dose

- of >10mg/day or equivalent), and continuous use within two weeks prior to enrollment;
18. Use of strong CYP3A4/CYP2C19 inducers, including rifampicin (and its analogues) and St. John's Wort, or strong CYP3A4/CYP2C19 inhibitors within two weeks prior to signing informed consent form;
 19. Known history of serious allergy to any monoclonal antibody or targeted anti-angiogenic drug;
 20. Severe infection within 4 weeks prior to the start of study treatment, including but not limited to hospitalization for infection, bacteremia or complications of severe pneumonia; oral or intravenous therapeutic antibiotics within two weeks prior to the start of study treatment (for example, subjects who are given with preventive antibiotics for prevention of urinary tract infection or exacerbation of chronic obstructive pulmonary disease are eligible for participation in the study);
 21. Congenital or acquired immunodeficiency (e.g., HIV infection);
 22. Combined hepatitis B and hepatitis C co-infection;
 23. Previous treatment with other PD-1 antibody or other immunotherapy against PD-1/PD-L1, or previous use of apatinib or sorafenib;
 24. Palliative radiotherapy for non-target lesions to control symptoms is allowed, but it must be completed at least 2 weeks prior to the start of study treatment, and the adverse event induced by radiotherapy must have resolved/improved to \leq CTCAE Grade 1;
 25. Attenuated live vaccine therapy administered within 28 days prior to the start of study treatment, or needed administration of such vaccines during SHR-1210 treatment or within 60 days after the last dose of SHR-1210;
 26. Treatment of other investigational product(s) within 28 days prior to the start of study treatment;
 27. Other factors that may affect the study results or lead to forced termination of the study early as judged by investigators, such as alcoholism, drug abuse, other serious diseases (including mental disorders) requiring concomitant therapy, with serious laboratory examination abnormality, with family or social factors, that may affect subject's safety.

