5.1.6.2.2. Principles of Management for Immune-Related Adverse Events

In overall principle, according to the severity of adverse reaction, interruption of SHR-1210 is taken as the main measure, resumption of SHR-1210 can be considered when the severity of adverse event has recovered to Grade 1 or below, and SHR-1210 should be discontinued permanently when serious Grade 3 or life-threatening Grade 4 adverse event occurs (For details, refer to Sections 5.1.6.1.2, 5.1.6.1.3 and 5.1.6.1.4 of this protocol which state criteria for dose delay, dose resumption, and permanent discontinuation of SHR-1210).

Management of immune-related adverse events should be based on the medical practice of the research center and the guidelines. The following provides the recommendations on management of immune-related adverse events (see Table 6), for reference. Recommended treatment procedures for common immune-related adverse events are detailed in APPENDIX 4 (Note that the rules for management of hepatic irAEs have been amended in this protocol [see Section 5.1.6.2.3 below]).

Table 6. Recommendations on Management of Immune-Related Adverse Events

| CTCAE Grade | Clinical treatment ^[3] | SHR-1210 treatment |
|----------------------------|--|--|
| Class 1 (Mild) | Close observation; symptomatic and supportive treatment | Continue |
| Grade 2 (moderate) | Close monitoring; Symptomatic and supportive treatment Local or systemic steroids treatment, 0.5-1 mg/kg/day, Prednisone or equivalent drugs | Interrupted temporarily, resume the medication when adverse reactions \leq Grade 1; Resuming the medication, except cutaneous and endocrine disorders |
| Grade 3 (severe) | Hospitalization is recommended. 1-2 mg/kg/day, Prednisone or equivalent drugs (i.v. or p.o.) If failed after steroids treatment for 3-5 days, consider addition of other immunosuppressants Specialized consultation is recommended | Interrupted temporarily; dose resumption must comprehensively consider risk/benefit ratio and be decided after discussion |
| Grade 4 (life threatening) | Intravenous 1-2 mg/kg Methylprednisolone. If failed after steroids treatment for 3-5 days, consider addition of other immunosuppressants Specialized consultation is recommended | Discontinued permanently. |

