5.1.6.2.3. Rules for Management on Hepatic Adverse Events of SHR-1210

Below are suggestions on management of hepatic AEs that may occur in the experimental arm during the SHR-1210 treatment period of this study:

- If the dose is delayed for 3-5 days and AST or ALT level is not improved but even exacerbated, cortisol, i.e., methylprednisolone 0.5-2 mg/kg/day or equivalent oral drugs, will be given;
- In case of AST or ALT >8 times of ULN, cortisol, i.e., methylprednisolone 1-2 mg/kg/day or equivalent oral drugs, will be given immediately, and meanwhile, a consultation from the department of gastroenterology is advised;
- If AST or ALT level is not improved but even exacerbated 3-5 days after the start of corticosteroids treatment, other immunosuppressants may need to be added, such as mycophenolate 1g BID;
- Once AST or ALT is decreased by one CTCAE Grade, the dose can be decreased gradually in no less than one month.

The study drug can be resumed when AST or ALT is recovered to baseline level, unless the criteria for permanent discontinuation is reached.

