5.3.2.2. Steroids

Local use of steroids is allowed, for example, topically external use, eye, nasal cavity, intra-joint and inhalation; corticosteroids for epinephrine replacement therapy are allowed; corticosteroids for treatment of adverse reactions are allowed; transient use of steroids for prevention and treatment of allergic reactions (prevention of allergy to contrast agents, or treatment of other allergic reactions) are allowed.

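### Section 5.3.1.2 has lost a negation: a list of prohibited drugs permits systemic corticosteroids above 10 mg/day and excepts only adverse-event treatment and short-term prevention

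*Protocol*

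**What the plan says.** Section 5.3.1.2 of the protocol is headed as a list of drugs prohibited for patients given SHR-1210. It holds three rules.

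- The first is a ban, "Subjects are not allowed to receive immunosuppressive therapies", with an exception for managing treatment-related adverse events.
- The second is the corticosteroid rule: "Systemic corticosteroid can be used at the dose of >10mg/day (Prednisone or equivalent), except for treatment-related AEs treatments or short-term preventive therapies".
- The third is a ban on live vaccines.

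Other sections also govern steroids:

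- **Section 4.2, item 17** excludes patients on "systemic corticosteroid therapy to achieve the objective of immunosuppression", with the same threshold of 10 mg/day prednisone or equivalent. Section 5.3.1.1 extends this to the treatment period: "Section 4.2 (Exclusion Criteria) of the protocol describes other drugs prohibited in this study".
- **Section 5.3.2.2** lists permitted steroid uses. Among them, "corticosteroids for treatment of adverse reactions are allowed", and so is "transient use of steroids for prevention and treatment of allergic reactions".
- **Section 5.1.6.2.2, Table 6**, recommends for Grade 2 immune-related events "Local or systemic steroids treatment, 0.5-1 mg/kg/day, Prednisone or equivalent drugs". For Grade 3 the dose is 1-2 mg/kg/day.
- **Section 5.1.6.2.3** directs that when AST or ALT exceeds 8 times the upper limit of normal, "methylprednisolone 1-2 mg/kg/day or equivalent oral drugs, will be given immediately".

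**The concern.** The corticosteroid sentence is a permission placed in a list of prohibitions. Taken literally, it allows systemic steroids above 10 mg/day for any ordinary reason. It then removes from that permission the two situations, adverse-event treatment and short-term prevention, in which the rest of the protocol wants steroids available. That is the reverse of the evident intent.

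The sentence does not expressly forbid steroids for adverse events, and those remain authorised elsewhere. The main harm is the unintended permission. The drug under test works by restoring T-cell activity, and the protocol restricts immunosuppression at entry and on study. Yet the only dose threshold written out in Section 5.3 places no ceiling on non-adverse-event steroid use, the use it was evidently meant to limit.

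The rule applies to every patient, because every patient is assigned SHR-1210. It also determines what is a deviation. Section 10.4.2 counts major deviations, and Section 11.2.2 has all deviations reviewed before database lock. A patient given 40 mg/day of prednisone for a reason unrelated to toxicity would comply with the sentence as it stands.

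**Working it through.** The plan gives no figure to reproduce. The check compares the sentence with each related rule under two readings: as written, and with the negation restored.

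| Related rule | As written | With "not" restored |
|---|---|---|
| Heading of 5.3.1.2 (prohibited drugs) | Contradicts: the sentence is a permission | Agrees |
| Preceding rule in 5.3.1.2 (ban, adverse-event management excepted) | Opposite direction, similar exception | Same direction, similar exception |
| 4.2 item 17, carried on study by 5.3.1.1 | Contradicts for steroids given to suppress immunity above 10 mg/day | Agrees |
| 5.3.2.2, adverse-event treatment and allergy prevention allowed | Leaves these uses out of its permission | Agrees on both uses |
| Table 6 and 5.1.6.2.3, steroids recommended or directed for immune-related and hepatic events | Leaves them out of its permission | Covered by the exception |

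Restoring one word reconciles the sentence with every row. No other text in the protocol corrects it.

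The next question is whether a 10 mg/day ban would need the adverse-event exception, since this bears on which reading was meant.

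1. The lowest systemic dose in Table 6 is 0.5 mg/kg/day prednisone. It equals 10 mg/day at 10 / 0.5 = 20 kg and exceeds 10 mg/day at any higher weight.
2. Inclusion criterion 9 requires a body surface area over 1.2 m². Under the Mosteller formula (an assumption; the protocol names no formula), BSA = √(height in cm × weight in kg / 3600). At 20 kg the required height is 1.2² × 3600 / 20 = 259.2 cm, so an eligible patient of 20 kg or less is implausible.
3. At assumed weights of 40 to 60 kg, the Table 6 doses are:
   - Grade 2 (0.5-1 mg/kg/day): from 0.5 × 40 = 20 to 1 × 60 = 60 mg/day.
   - Grade 3 (1-2 mg/kg/day): from 1 × 40 = 40 to 2 × 60 = 120 mg/day.

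A 10 mg/day ban without the exception would therefore block Table 6 systemic treatment in essentially every eligible patient. The exception clause fits a ban and has no sensible role in a permission. This arithmetic supports the reading; it does not measure how much steroid use outside adverse events would occur.

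**The case against.** The strongest reply is that the practical gap is narrow. The heading and the neighbouring bans signal the intent, so an investigator is unlikely to be misled. The section separately bars immunosuppressive therapy. Exclusion 17, carried on study by Section 5.3.1.1, already covers steroids above 10 mg/day given for immunosuppression. Adverse-event treatment is not endangered, because a permission that omits a use does not cancel sections that grant it. No inferential quantity is touched.

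Much of this is fair, and it limits the weight of the point:

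- Exclusion 17 does narrow the gap, but only for immunosuppressive intent and only by cross-reference from an entry criterion. Systemic use for other purposes is left to the faulty sentence.
- The conflict with the adverse-event sections is weaker than the conflict with the heading and with exclusion 17. It arises on the ordinary reading of the exception and is not an express prohibition.
- The dose arithmetic holds for the systemic doses in Table 6 only. That table's Grade 2 row also offers local steroids, and Appendix 4 suggests 10-20 mg prednisone for arthralgia, whose lower end is not above 10 mg/day.
- Dexamethasone is listed as prohibited in Section 5.3.1.3, which reduces the permission. The same section, however, contemplates dose adjustment if a strong CYP3A4 inducer must be used.

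None of this makes the sentence correct. Many readers would guess the intended rule, but a monitor cannot cite a deviation from a rule that says the drug may be used.

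**Conclusion.** The concern holds. The corticosteroid sentence in Section 5.3.1.2 states the opposite of the evident rule. It contradicts its own heading and, for immunosuppressive use above 10 mg/day, exclusion 17 as carried on study. On its ordinary reading it also sits against the adverse-event steroid provisions.

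The gap left open is systemic use above 10 mg/day that is neither for an adverse event nor for immunosuppression and falls outside Section 5.3.2.2. The number of patients it could affect cannot be derived from the protocol. Sample size, error rates and the two-stage decision rule are unaffected. The consequences are for patient safety, uniform conduct and the classification of deviations, so it should be corrected.

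The conclusion rests on the wording and placement of the rules. The body weights and the Mosteller formula are assumptions used only as a plausibility check.

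**What to change.** Replace the sentence in Section 5.3.1.2 with:

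> Systemic corticosteroids must not be given above 10 mg/day of prednisone or equivalent, except to treat a treatment-related adverse event, as short-term prophylaxis, or for a use permitted in Section 5.3.2.2.

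Naming Section 5.3.2.2 keeps replacement therapy and allergy treatment permitted, so the corrected ban creates no new conflict there. No other section has to change. The cost is one sentence in a protocol amendment, with no effect on design, sample size or analysis.
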